1.14 Will participants be randomized?

Yes

- **1.15** Will any of the following be used to collect information from the participant or others?
 - Screening questions or screening/eligibility questionnaires
 - Surveys
 - Questionnaires
 - Stimuli
 - Any other written assessments

Yes

Attachment Name	Category	Version	Date Attached
Patient survey intervention Aim3 v8.docx	Subject Data Collection Instruments	1	05/29/20
Patient survey control Aim3 v1.docx	Subject Data Collection Instruments	1	05/29/20
Clinician survey SDM Aim 3 pre post May2020.docx	Subject Data Collection Instruments	1	05/29/20

- 1.16 Does this project involve creating any audio, video, or photographs? Yes
- 1.17 Does the study include any form of deception (e.g., providing participants with false information, misleading information, or withholding information about certain study procedures)?
 Examples:
 - Procedure includes a cover story that provides a plausible but inaccurate account of the purposes of the research.
 - Participants will be provided with false information regarding the particular behaviors of interest in the research.
 - Procedures include a confederate pretending to be another participant in the study.
 - Participants will be told that the research includes completion of a particular task, when in fact, that task will not be administered.
 - · Study is designed to introduce a new procedure (or task) that participants are not initially told about.

No

- **1.18** Indicate any payments or reimbursements to participants (check all that apply)
 - · Gift or Debit Card
- 1.19 Does this study have a plan to have an individual or committee review combined data from all participants on a periodic basis (such as summary or aggregate safety and/or efficacy data)?

 Yes, but it's not described in an attached protocol

A Data and Safety Monitoring Committee (DSMC) will be convened for this trial to review outcomes data at least every 6 months following study activation. The DSMC will consist of no fewer than 3 members including 2 clinical

investigators and a biostatistician. All DSMC members will be familiarized with the research protocols and plans for data safety and monitoring. Like investigators, DSMC members are subject to university policies regarding standards of conduct. Individuals invited to serve on the DSMC will disclose any potential conflicts of interest to the trial principal investigator and/or appropriate university officials, in accordance with institution policies. Potential conflicts that develop during a trial or a member's tenure on a DSMC must also be disclosed. The DSMC report will be prepared by the study statistician with assistance from the study team, will be reviewed by the DSMC.

- **1.20** What have you done to minimize any risks?
 - Other It is possible participants may feel uncomfortable with some of the questions or photos in the tool. They can skip any questions they do not want to answer, or skip parts of the tool. Another risk if a participant joins the study is that confidential information about them may be accidentally disclosed. Their information will be secure, in password-protected network drives that only the study team can access. We will identify participants by a number and not by their name. We will report our findings in summary form and not linked to any one person.
 - **1.21** What are the potential benefits related to this project for:
 - the participant (if any)
 - benefits to society (if any)

This project may not present a direct benefit to the participants. Some breast cancer patients randomized to the BREASTChoice arm of the Aim 3 trial may benefit from receiving additional information about breast reconstruction, their potential risk of complications, and evaluating their preferences. Society may benefit from the development of new clinical communication tools for discussing breast reconstruction options with patients and clinicians.

1.22 Provide a summary of the analysis methods you will use, including, if applicable, the data points or outcomes you will analyze.

Descriptive statistics will be calculated for demographic and clinical characteristics (race, age, comorbidities, etc.) and for knowledge, preference concordance, decisional conflict, and Collaborate.

The primary endpoints of knowledge, preference concordance, and decisional conflict will first be evaluated with univariate analyses through the use of t-tests and chi-square analyses as appropriate. We will explore the use of transformations and non-parametric alternatives for these responses if necessary. We will use generalized linear mixed models to explore differences between patients randomized to BREASTChoice and to the control arm. Models will be adjusted for important clinical and demographic variables and will include relevant interactions. Specifically, we will include an interaction between group (i.e., BREASTChoice or control)and time, to test for differences in randomized group over time that could be due to changes in surgeon practices. A random effect for surgeon will also be included in the model. Missing data will be handled through imputation, and associations between covariates and the missing indicator will be explored. The same analytic procedure will be used to examine the impact of BREASTChoice on patient engagement (CollaboRATE).

A secondary goal is to explore whether the intervention is associated with fewer high-risk patients choosing reconstruction. Patients will be considered high-risk if their risk exceeds 2 times the population average.38 We will explore whether age or race modifies the association between intervention and decision quality (knowledge and preference concordance). Descriptive statistics will be calculated for these outcomes, and associations will be assessed using appropriate chi-square or Fisher's exact tests.

We also will explore whether provider intention to engage in shared decision making increases during the trial, by examining changes in the mean of the CPD-Reaction scale, through the use of the Wilcoxon signed-rank test. Preferred decision role will also be assessed through chi-square or Fisher's exact tests.

Provide the rationale or power analysis to support the number of participants proposed to complete this study. The sample size needed to detect an effect size of 0.3 and power of at least 80% in decisional conflict, comparable to what was seen in a similar study,122 is 170 per group. With this sample size,the study will be adequately powered to detect at least a 15% difference in the percent of patients with knowledge scores > 50%, assuming that the control group percentage of patients scoring > 50% is 34%.

If instead we wish to compare differences in knowledge score between groups, this same sample size will provide > 90% power to detect a difference of a mean 10 points. The effect size was also chosen based on an RCT aiming to reduce decisional conflict about breast reconstruction via online decision aid (DA). That study found that at 1 and 6 months, the DA group had significantly less decisional conflict (effect sizes of 0.35and 0.29, respectively). The DA group scored on average at levels consistent with having made a decision, while the control group still had scores reflecting indecision. These differences can lead to clinically meaningful differences in quality of life in cancer patients. In addition, the DA group had a reduction in decisional conflict to a level below a cutoff for clinically significant scores (score <25), while the control group reported clinically significant decisional conflict (score > 25).124 Thus, our effect size is both statistically and clinically meaningful.

- 1.25 Will any data from this project be stored for use in future research studies? No
- 1.26 Does this project involve the collection or use of biological samples or genetic data? No

1.27 Are you requesting institutional certification to contribute human data or samples to a repository or database for broad sharing (public or restricted access)?

No

2. Participants

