Decisions about whether to have breast reconstruction following a mastectomy due to breast cancer, when to have it, and what type of reconstruction are often discordant with patients' personal preferences about risk, appearance, recovery, and number of surgeries. There are currently no reliable methods for integrating patient-specific information into the clinician-patient encounter to personalize these decisions. Incomplete or insufficient information could lead to unexpected complications, additional operations, and decision regret. Compared to most elective procedures, major complications from breast reconstructive surgery are high. As many as 50% of patients having reconstruction, experience wound complication and about 15% of patients experience complications that require additional surgeries. For some patients, complications lead to 15-20 additional procedures.

Patients often lack knowledge of complication risks for reconstructive surgery. This lack of knowledge can lead to poor satisfaction and regret. In one study, only 15% of patients understood potential risks and complications of post-mastectomy reconstruction options. Additionally, gaps exists in how breast reconstruction decision – making is addressed between clinicians and different populations. For example, Black women report unmet information needs and have greater knowledge deficits about reconstruction. Older (65+) women are less likely to be offered reconstruction compared to younger women.

Due to the higher risk of major complications from reconstructive surgery, and gaps in the decision making process, the BREASTChoice (Breast Reconstruction Education And Support Tool) tool was developed in our earlier work. The BREASTChoice tool helps women, who are undergoing a mastectomy, make decisions with their clinician about reconstructive surgery based on their personal risk factors and preferences.

BREASTChoice incorporates personalized, predictive risk analytic modelling, developed and validated using institutional and national claims data from over 17,000 patients. The tool is an interactive website and can be sent through My Chart and integrated into the electronic health record. The formative work on this tool and subsequent pilot testing demonstrated an increase in self-reported knowledge for patients in the intervention group, and usability was high.

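### The test of reconstruction choice in high-risk patients rests on an undefined cut-off and a probably small subgroup; define the risk and add a model using all randomised patients

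*Combined protocol and SAP*

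**What the plan says.** Section 1.22 states: "A secondary goal is to explore whether the intervention is associated with fewer high-risk patients choosing reconstruction". The group is defined by "Patients will be considered high-risk if their risk exceeds 2 times the population average". For this goal and the age and race questions beside it, the plan offers descriptive statistics and then "associations will be assessed using appropriate chi-square or Fisher's exact tests".

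The section does not say which complication the risk refers to, which population supplies the average, what that average is, or how many patients should qualify. The sentence carries citation number 38, but the list in section 1.6 ends at 23, so the source of the rule cannot be seen.

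The only complication rates given are in section 1.5: "As many as 50% of patients having reconstruction, experience wound complication", and "about 15% of patients experience complications that require additional surgeries". Neither is linked to the cut-off. Eligibility in section 1.7 is not enriched for surgical risk. The sample size of 170 per group was set for other outcomes: "The sample size needed to detect an effect size of 0.3 and power of at least 80% in decisional conflict", with a further calculation for knowledge.

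**The concern.** A cut-off set at a multiple of an average behaves very differently depending on that average. Doubling a common risk gives a threshold near or at certainty. Doubling a moderate one gives a threshold in the upper tail. Because the plan leaves the outcome open, one permissible reading cannot be carried out, and the other leaves a group whose size depends on an unreported spread of predicted risk.

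Personalised risk is central to this tool, so readers will look at this result. A non-significant test in a few dozen women or fewer could be taken to show that the tool does not change choices in those at high risk.

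There is a related gap. Sections 1.5 and 1.13 describe the risk calculation only inside BREASTChoice, and section 1.13 lets participants edit their health information there. The plan does not say how risk is obtained for control patients. If tool-based values were used for the intervention arm, membership of the group could partly reflect information changed after randomisation.

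**Working it through.** **Inputs from the documents.** 170 per group, 340 in total; a cut-off of twice the average; rates of up to 50% and about 15% (section 1.5).

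**Assumed, because not given.** Two-sided alpha 0.05; 1:1 allocation; calibrated predicted risk with a beta distribution, a trial mean equal to the reference average and a c-statistic of 0.60 to 0.80; 60% of high-risk control patients choosing reconstruction.

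**1. The plan's own figure.** For a standardised difference of 0.3 and 80% power, n = 2(1.960 + 0.842)²/0.3² ≈ 175 per group. The stated 170 is within 3% of this and gives power of 0.79. The knowledge calculation (34% versus 49%) needs 169 per group. So 340 is a fair base. The plan gives no expected number of high-risk patients to reproduce.

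**2. Cut-off.** 2 × 50% = 100%, which no probability exceeds. 2 × 15% = 30%, which is reachable.

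**3. Number above 30% when the average is 15%.**

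| c-statistic | Share above (beta) | Of 340 (beta) | Of 340 (logit-normal) |
|---|---|---|---|
| 0.60 | 0.3% | 1 | 2 |
| 0.65 | 3.0% | 10 | 13 |
| 0.70 | 7.5% | 25 | 27 |
| 0.75 | 11.7% | 40 | 40 |
| 0.80 | 15.2% | 52 | 49 |

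Higher averages give fewer: at a c-statistic of 0.70 (beta), about 17 patients at a 25% average, 7 at 35% and 1 at 45%. With no distributional assumption, all that can be said is that no more than half of a population can exceed twice its own mean (Markov), so the range above rests on the assumed shape.

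**4. Power and precision in the subgroup.** The power columns are for Fisher's exact test. The last column is 1.96 × √[(0.6 × 0.4 + 0.4 × 0.6)/n], the approximate 95% half-width for the difference when the true rates are 60% and 40%.

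| Per arm (n) | Power, 60% v 40% | Power, 60% v 30% | Half-width |
|---|---|---|---|
| 6 | 2% | 4% | ±55 points |
| 15 | 10% | 23% | ±35 points |
| 26 | 21% | 48% | ±27 points |

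By normal approximation, with 51 high-risk patients in total, 80% power needs a fall of about 38 points from 60%; with 34, about 45 points.

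**5. A model in all 340 patients.** Simulated trials compared the subgroup test with a logistic model on arm, continuous risk and arm × risk, testing the arm difference at high predicted risk. Ranges span the scenarios tried.

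| True effect | Model | Subgroup test |
|---|---|---|
| Grows with risk | 46–52% | 11–38% |
| Same at every risk | 17–29% | 4–9% |
| Only above the cut-off (SD of risk 10 points) | 21% | 29% |

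Type I error of the model was near 5%. Part of its advantage arises because Fisher's test is conservative in small groups: its type I error was 1.6% at a 15% average with an SD of 7 points.

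**The case against.** A reader might infer that the cut-off selects nobody, or only a handful, so that the trial cannot answer the goal and a null result is almost certain. The documents do not support this. The 50% figure is an upper rate, it describes women who had reconstruction, and section 1.22 never ties it to the cut-off. At 15%, a model that discriminates well would put about 40 to 52 patients above the threshold. The reference average may come from an outside population, such as the cohort of over 17,000 patients used to build the model, which could move the count either way. Power of 20% to 50% for large differences is low, but it is not certain failure.

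The choice of analysis is also open to challenge. If the tool acts only on women above the cut-off, the subgroup test is the more powerful. An interaction coefficient on its own tests whether the effect varies with risk, which is a different question. Replacing the cut-off with a top quartile would lower the bar: at a 15% average and an SD of 7 points it starts at about 19%, or 1.3 times average. That is a matter of judgement.

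Finally, the goal is worded as exploratory, no power is claimed for it, and descriptive statistics are already planned.

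All of this stands. It limits the claim to an incomplete definition and poor precision, and it argues for adding a model and keeping the subgroup. It does not supply the missing definition or make the subgroup test informative.

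**Conclusion.** The concern holds in a limited form. The definition is incomplete: on one rate quoted in the plan the threshold is unreachable, and on the other it selects roughly 0.3% to 15% of 340 patients. Even at the top of that range, about 26 per arm, power is about 21% for a 20-point difference and 48% for a 30-point difference. A non-significant result would therefore be uninformative.

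The 100% threshold is plain arithmetic, conditional on 50% being the average used. The counts rest on the assumed distribution, the c-statistic range and a trial mean equal to the reference average. The power figures also rest on the assumed 60% in controls. The model's advantage depends on how the effect varies with risk. The primary endpoints are unaffected.

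**What to change.** In section 1.22:

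1. Name the complication whose predicted risk is used, the reference population and its average. State the expected number of high-risk patients per arm.
2. Calculate risk in both arms with the same model from baseline record data, not from values edited in the tool.
3. Add a logistic model of reconstruction choice in all randomised patients on arm, continuous baseline predicted risk and arm × risk. Report the arm difference with a 95% CI at high predicted risk, for example at the 90th percentile, and at twice the average where that is reachable. The quantity of interest is this difference, not the interaction p-value.
4. Keep the subgroup at twice the average as a descriptive table with counts per arm and a CI. State that a non-significant subgroup test will not be read as no effect.

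The cost is a few sentences, one model, and a risk calculation for control patients that the comparison needs in any case. No extra patients are required. The downside is that the model assumes a smooth change of effect with risk and loses power if the effect exists only above the cut-off. The goal remains exploratory.

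### Does it matter that the plan does not say which form of knowledge, or which test, decides a primary endpoint?

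*Combined protocol and SAP*

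**What the plan says.** Section 1.22 names three primary endpoints: knowledge, preference concordance and decisional conflict. They "will first be evaluated with univariate analyses through the use of t-tests and chi-square analyses as appropriate". The next sentence adds: "We will explore the use of transformations and non-parametric alternatives for these responses if necessary". No criterion is given for leaving the standard test.

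The modelling step is then introduced: "We will use generalized linear mixed models to explore differences between patients randomized to BREASTChoice and to the control arm". On covariates the plan says "Models will be adjusted for important clinical and demographic variables and will include relevant interactions", and it specifies one interaction: "we will include an interaction between group (i.e., BREASTChoice or control)and time, to test for differences in randomized group over time". A random effect for surgeon is included.

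The power rationale after section 1.22 bases 170 per group on decisional conflict (effect size 0.3, power at least 80%). It then covers knowledge twice. The first form is binary, with a control rate of 34% and "at least a 15% difference in the percent of patients with knowledge scores > 50" per cent. The second is a mean score: "If instead we wish to compare differences in knowledge score between groups, this same sample size will provide > 90% power" for a difference of 10 points. The SD of the score is not given. Neither section states the significance level or says which form of knowledge is primary.

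**The concern.** The wording presents the form of a primary endpoint as a choice still to be made. Knowledge could be tested by chi-square on the share above 50% or by t-test on the mean. Either could be followed by an adjusted model of the same arm difference. If these disagree, a reader cannot tell from the plan which one is the trial's answer. If the choice were made after seeing results, and the significant one reported, the 5% error rate for that endpoint would no longer hold.

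The monitoring arrangement in section 1.19 sharpens the worry. A committee is "to review outcomes data at least every 6 months following study activation", and its report is prepared by the study statistician with help from the study team. The people likely to settle the choice might therefore see outcome data first.

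**Working it through.** **Inputs.** From the power rationale: 170 per group; effect size 0.3 for decisional conflict; 34% control rate and a 15-point difference, so 49%; a 10-point mean difference with more than 90% power. Assumed because not stated: two-sided 5%, and normal knowledge scores with a common SD.

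**Reproducing the plan's figures.**
- Decisional conflict: n = 2(1.960 + 0.842)² / 0.3² = 174.4, so 175 per group. With 170, power is Φ(0.3 × √85 − 1.960) = Φ(0.806) = 79.0%. This agrees with the stated 170 and 80% to within rounding.
- Knowledge above 50%: the standard error is √(2 × 0.415 × 0.585 / 170) = 0.0534 under the null and √((0.34 × 0.66 + 0.49 × 0.51) / 170) = 0.0528 under the alternative. Power = Φ((0.15 − 1.960 × 0.0534) / 0.0528) = Φ(0.857) = 80.4%.
- Mean knowledge: more than 90% power for 10 points requires SD ≤ 10 / ((1.960 + 1.282) × √(2/170)) = 28.4. The SD is not given, so this figure can be bounded but not confirmed.

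**Putting both forms on one scale.** For normal scores, 34% against 49% above a fixed cut is a shift of z(0.66) − z(0.51) = 0.412 − 0.025 = 0.387 SD. The t-test then has noncentrality 0.387 × √85 = 3.57 and power of about 94.5%.

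**How often the two tests differ.** In a simulation of 40,000 trials with both tests run on the same data, the t-test was significant in 94.4% and the chi-square in 81.1%. They differed in 15.0%: 14.2% t-test only and 0.8% chi-square only. The net difference, 14.16 − 0.83 = 13.3 points, equals the power gap (94.4 − 81.1 = 13.3). About 94% of the disagreements (14.16 / 14.99) are therefore the t-test succeeding where the dichotomised version falls short. Estimates in opposite directions are very rare: the chi-square's z is centred at 0.15 / 0.0528 = 2.84, and its chance of falling below zero is about 0.2%.

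**Sensitivity.** At 34% against 49%, discrete scores with 5, 10 or 20 items give 12.8% to 14.6%, and a Yates correction gives 17.7%. At the plan's other effect, 10 points on the mean, the result depends on the SD:

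| SD | Tests differ |
|---|---|
| 15 | 0.2% |
| 20 | 4.1% |
| 25 | 13.7% |
| 28.4 | 19.3% |

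Every SD in the table is compatible with the stated power of more than 90%.

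**Under no effect.** Each test alone is significant in 4.9% of simulated trials, so each is valid as written. At least one is significant in 7.7%. A bivariate-normal calculation with correlation 0.773 between the two statistics gives 8.0%.

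**The case for a change.** The strongest case is that two tests remain even on the reading kindest to the plan. The order of the text, and its use of the models to explore, favour the univariate step; but for knowledge that step is itself either a chi-square or a t-test. The disagreement figure at 34% against 49% survives changes in the score model, a few sentences would settle the matter, and no patients or analyses would be lost.

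The textual point stands: the form of knowledge is left open. The consequence does not go as far as it first appears.

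- The inflated error rate needs a rule of claiming whichever form is significant. No passage contains one. The plan sets an order, and its sample size matches a plain two-group comparison, which gives decisional conflict a natural deciding test.
- The monitoring point is inference. Section 1.19 describes routine report preparation. It does not say that results are shown by arm, or that those preparing the report choose the endpoint form.
- Setting the univariate test against the adjusted model cannot be sized from the documents. It needs the variance explained by covariates, the number of surgeons and the between-surgeon variance, and none is given. I place no weight on figures built from assumed values.
- The covariates are not wholly open: the start of section 1.22 names race, age and comorbidities among the characteristics to be described. That list is open-ended and meant for description, so it is only partial guidance.
- The group-by-time term has a stated purpose, to detect drift from changing surgeon practice. Calendar time is the natural reading, and how it is coded is an ordinary modelling decision.

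**Conclusion.** The plan leaves a detail unstated, but it does not prescribe a wrong analysis. Both forms of knowledge are reasonable, both hold the 5% level, and the more powerful one, the mean score, is already in the plan. A remedy could only ask the team to write down a choice among analyses it already lists. Section 1.22 is a methods summary in one site's application, and analysts working from it can settle this sensibly.

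The size is as follows. The two forms differ in significance in about 15% of trials at 34% against 49% (roughly 13% to 18% across the score models tried), and in 0.2% to 19% at a 10-point difference for SDs from 15 to 28.4. Nearly all of the 15% is power lost by dichotomising. The false-positive rate would be about 8% only if either form could be claimed after the fact. These figures assume two-sided 5% and 170 analysed per group; apart from the discrete-score runs, they also assume normal scores with a common SD. No change to the plan follows.
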